CLINICAL STUDY PROTOCOL

Innovation in the Treatment of Persistent Pain in Adults with NF1: Implementation of the iCanCope Mobile Application- Clinical

Trial

NCT04561765

Protocol Number

2000029045

Principal Investigator

[name]

Sponsor

Department of Defense

Protocol Version

9 November 2020

version 3

Confidentiality Statement:

Study Personnel

Principal Investigator

[name]

Email: [contact]

Synopsis

Study Purpose

OBJECTIVES & HYPOTHESES: To evaluate whether the *iCanCope-NF* program will reduce pain (pain severity and pain interference) in adults with NF1. We hypothesize that by customizing the CBT and the MBAA in the mobile application for adults with NF1, individuals will engage regularly, thus acquiring a new set of skills to facilitate their own pain self-management, while pain will decrease.

SPECIFIC AIM:

To determine the feasibility and preliminary effectiveness of *iCanCope-NF* in adults (n=108) with NF1 suffering from pain in a RCT.

Primary Objective

To evaluate whether the *iCanCope-NF* program will reduce pain (pain severity and pain interference) in adults with NF1.

Secondary Objectives (if applicable)

n/a

General Design Description

A 1x3 pilot randomized control trial (RCT) (*iCanCope-NF*, *iCanCope-NF* +Contingency Management (CM), Control Group) will be conducted with 108 adults with NF1 who suffer from pain.

Study Date Range and Duration

We predict the pilot RCT to take 18 months to complete (February 1, 2021 to August 2022). The patient networks that we are recruiting from have over 25000 adults across both groups. A conservative estimate of 20% of individuals should be within the appropriate age criterions (~5000). Given that we are seeking to fulfill 36 in each group for a total of 108 for the Pilot RCT and taken in account of a conservative 20% refusal rate. We should not encounter an issue with total number of individuals enrolled within the study within the time frame.

Number of Study Sites

There will be three study sites for this study: Yale School of Medicine, Connecticut Children's Hospital (Hartford, CT), and The Hospital of Sick Children (Toronto, Canada).

Yale School of Medicine: The PI will run the entire clinical trial through Yale School of Medicine. All potential participants will be recruited, consented, orientated to a treatment group (if applicable).

Connecticut Children's Hospital (Hartford, CT): will consult but will not have access to the PHI data

The Hospital of Sick Children (Toronto, Canada): will host the server of the iCanCope and the dashboard of the server but will not see any personal PHI.

Primary Outcome Variables

1. Engagement Activity

Total minutes logged on the mobile application will be evaluated between the two groups using the mobile application.

2. Pain Severity

A comparison within groups change of pain severity measured by the Brief Pain Inventory-Short Form. Respondents rate items on a 0-10 scale to indicate the pain severity and interference, and the total score is the mean of each subfactor. The higher the score indicates more severity and interference of pain.

3. Pain Interference Index

A comparison within groups change of pain interference measured by the Pain Interference Index Scale. Respondents rate items on a 0-6 scale to indicate how much pain has interfered with various activities, and the total score is the mean of the six items. Where 6 indicates high interference.

Secondary and Exploratory Outcome Variables (if applicable)

Secondary Outcome Measures:

1. Treatment Services Review what are perceptions of satisfaction across groups exposed to the iCanCope mobile application using an The Treatment Services Review (TSR)
2. Anxiety comparison within change of generalized anxiety measured by the generalized anxiety disorder scale (GAD-7). After reading each statement, one of four choices are provided and respondents can select one response (1=not at all sure, 2=several days, 3=over half days, 4=nearly every day). Each column is then added, and a total score is obtained, with scores falling into four levels of anxiety, including minimal (1-4), mild (5-9), moderate (10-14), and severe (15-21)
3. Sleep functioning comparison within change of sleep quality measured by the PROMIS Sleep inventory. The higher the total score, the more severe the symptom. Total scores less than 24 suggest no to slight sleep disturbance, 24-28 suggest mild disturbance, 29-38 moderate disturbance, and greater than 38 severe sleep disturbance
4. Short Form/Quality of Life the Short form survey 20- will measure quality of life across 8 subscales on respondent burden (Physical Functioning, Role-Physical,

Bodily Pain, General Health, Vitality, Social Functioning, Role-Emotional, and Mental Health). Scores were transformed linearly to 0-100 scales, with 0 and 100 assigned to the lowest and highest possible scores, where high value indicated better functioning.

5. Chronic pain acceptance Chronic Pain Acceptance Questionnaire-Revised (CPAQ-Revised) 20-item scale designed to measure acceptance of pain. The acceptance of chronic pain is thought to reduce unsuccessful attempts to avoid or control pain and thus focus on engaging in valued activities and pursuing meaningful goals will be measured across all groups. The items on the CPAQ are rated on a 7-point scale from 0 (never true) to 6 (always true). To score the CPAQ, add the items for Activity engagement and Pain willingness to obtain a score for each factor. To obtain the total score, add the scores for each factor together. Higher scores indicate higher levels of acceptance
6. psychological inflexibility Psychological Inflexibility in Pain Scale (PIPS) 16-item scale used to assess psychological inflexibility (i.e. avoidance, acceptance, fusion, values orientation, dirty discomfort) in people with chronic pain will be measured across all groups. Respondents are asked to rate items on a 7-point scale that ranges from 1 (never true) to 7 (always true). Higher scores indicate greater levels of psychological inflexibility.

Other Pre-specified Outcome Measures:

1. Mindfulness based alternative approaches (MBAA) Do individuals with NF1 utilize the MBAA more readily because they are on the mobile application, via Five Facet Mindfulness Questionnaire. 39-item self-completed questionnaire measuring the five facets of mindfulness: Observing (8 items), Describing (8 items), Acting with awareness (8 items), Non-judgmental (8 items), and Non-reactive (7 items). Participants rated the items on a five-point Likert scale (1 = never or very rarely true to 5 = very often or always true), each facet score ranges from 8 to 40, except for the non-reactive facet which ranges from 7 to 35.

Study Population

A convenience sample of 108 adults with NF1 aged 18-34 will be recruited through mail merge and emails, Internet advocacy web forums (NF Network, NF Northeast:

Number of Participants

A convenience sample of 108 adults with NF1 aged 18-34 will be recruited through mail merge and emails, Internet advocacy web forums (NF Network, NF Northeast: see letters of support).

Power Analysis: An a priori power analysis conducted through G*Power (Universität Kiel, v. 3.1.9.2) estimated a conservative sample size analysis for the RCT. We are expecting a total of 140 participants, given the length of the trial, we estimate 20% attrition rate of the final sample, giving us a total sample of (n=36) per group, for a final sample size of 108.

The power analysis is based on previously utilized research in which estimated effect sizes ranged from 20 to 40 individuals per group (52). We will attempt to enroll equal numbers of male and female individuals to evaluate gender differences through urn randomization process.

52. Hancock, G. R. and R. O. Mueller, Eds. (2010). *The Reviewer's Guide to Quantitative Methods. Power Analysis*. New York, NY, Routledge.

Visit Schedule Table (Optional)

n/a

Study Flow Chart (optional)

see flow chart below

Abbreviations

Abbreviation	Explanation
--------------	-------------

Glossary of Terms

Glossary	Explanation
----------	-------------

Table of Contents

Synopsis.....
Study Purpose
Primary Objective
Secondary Objectives (if applicable)
General Design Description.....
Study Date Range and Duration
Number of Study Sites
Primary Outcome Variables
Secondary and Exploratory Outcome Variables (if applicable)
Study Population.....
Number of Participants
Visit Schedule Table (Optional)
Study Flow Chart (optional)
Abbreviations
Glossary of Terms.....

1.1 Statement of Compliance

This document is a protocol for a human research study. The purpose of this protocol is to ensure that this study is to be conducted according to the Common Rule at 45CFR46 (human subjects) and other applicable government regulations and Institutional research policies and procedures.

2.1 Background

Background: Neurofibromatosis Type 1 (NF1) is an autosomal dominant genetic condition affecting 1 in 2500 individuals (1). NF1 was originally classified as a tumor predisposition

syndrome based on the propensity of affected children and adults to develop benign and malignant tumors (2,3). Over 50% of individuals with NF1 report significant pain and discomfort (4,5) which can be associated with tumors, but is often not localized to a structural lesion, thus presenting treatment challenges for patients and their medical caregivers. Moreover, the increased pain in this population can negatively impact an individual's perceived quality of life (6,7). Due to the complexity of the disorder (e.g., location, severity, number, and type of tumors), there are limited effective therapeutic options for treating pain (3). In this regard, tumor-related pain is primarily managed by either surgery or medication (8,9). To date, there has been limited research exploring the daily impact of living with persistent pain from a qualitative perspective by the individual living with NF1 and evaluating NF1 pain and treatments.

Barriers to Pain Treatment: Individuals suffering from persistent pain have multiple potential barriers to obtaining comprehensive pain specific treatment including: (a) difficulty accessing these services (e.g., no services available in many geographic areas, long wait times); (b) limited availability of trained professionals such as psychologists, particularly in non-urban centers; (c) patient-related issues (i.e., psychological, communication, and attitude); (d) current health care system barriers, (i.e., reimbursement, costs of treatment) and (e) limited access to self-management techniques (10-14). Self-management can be defined as the individual's ability to manage the symptoms, treatment, physical, and psychological consequences and lifestyle changes inherent to living with a chronic illness (15). Self-management interventions that provide individuals with disease-specific knowledge, strategies to manage symptoms such as pain (e.g., cognitive-behavioral therapies; CBT), and social support are needed to promote optimal health outcomes.

Cognitive Behavior Therapy and Pain Treatment: Cognitive Behavior Therapy (CBT) uses assessment and evaluation of current behaviors to identify problem behaviors and develop skills to manage situations as well as to cope with difficult thoughts and feelings (16,17). CBT typically incorporates normalization of the patient's experience through education, training in strategies for managing disease-related symptoms and other stressors, enhancing self-efficacy, as well as guidance on developing and implementing a long-term self-management plan (18-19). Studies have documented the efficacy of CBT across a wide range of diseases and disorders. A recent meta-analysis showed that the most successful interventions in improving pain and associated functional impairments in adults with chronic pain are rooted in CBT (20). It is well documented that the skills learned through CBT continue, sometimes even increase, after treatment has been completed (21,22). To date, there has been little peer reviewed research within the NF1 population utilizing CBT to treat pain symptoms. CBT like many other psychotherapies has multiple disadvantages: (1) mental health clinicians and practitioners require extensive training in both CBT and pain treatment, (2) limited access to appropriate care of trained clinicians, and (3) formalized face-to-face treatment is relatively expensive. Furthermore, mind-body alternative approaches (MBAA) (i.e., yoga, mindfulness), can have impact on pain intensity and have been found to alter pain experience (23). Research has shown that when CBT and MBAA interventions are combined, they can be effective in decreasing negative emotional

responses to pain, decreasing perceptions of disability, and increasing orientation toward self-management during treatment (24,25). A recent meta-analysis confirmed a combination of CBT and MBAA to be as effective as face-to-face CBT with patients suffering from persistent and chronic pain (26). This same review showed patients preferred mobile-based therapy and had more consistent usage than face to face CBT.

Mobile Technologies to Enhance Delivery of Pain Self-Management Care: Mobile technologies can be applied to enhance the accessibility of pain self-management therapies (27,28). In addition to improving access, these technologies can empower individuals to take an active role in managing their condition by providing "in the moment" access to pain coping strategies (29). Additionally, a systematic review showed that incorporating self-management strategies for persistent pain within standard treatment increases treatment efficacy and patient buy-in (30). Over 78% of U.S. adults own or have access to Smartphones; therefore, smartphones offer an ideal platform to prompt practice of CBT-based coping skills in the moment. This technology can be leveraged to build a tailored self-management program that emphasizes empowerment, facilitates the creation and tracking of personalized goals, and offers a peer-based social support platform to prompt practice of CBT-based coping skills as needed. In the current mobile marketplace, there are over 120 pain applications, but few are empirically valid (31). The iCanCope mobile and web-based program provides personalized goal setting to improve pain and function, CBT-based pain self-management training and rehearsal, and peer-based social support, while providing key health information and coping skills to individuals. The iCanCope mobile and web-based self-management program has been empirically evaluated for multiple painful diseases in children and adolescent populations (32,33). Yet, with any mobile application poor adherence is a common problem which can limit the effectiveness of intervention, and the iCanCope mobile application has not been tested within adults. One approach to combat poor adherence and increase patient engagement and retention is contingency management (12,34,35)

Contingency management: Contingency management (CM) arranges systematic application of behavioral consequences of desired behavior and withholds reinforcement of undesired behaviors (36). CM interventions are based on extensive basic and clinical science intervention research supporting that training in a CM setting can develop and improve real world skills; therefore, predicting skill use and quality of use in real life (37,38). By using points, levels, prizes or other rewards, and well-established reinforcement schedules, individuals are actively engaged (39-41) and CM can encourage individuals to practice behavioral change in a novel and entertaining way (42-44) and can be generalized to the person's natural environment and enhance motivation for change.

Neurofibromatosis and Pain: Based on my current findings (in press), over 15% of adults with NF1 are currently using pharmacological interventions and 60% had at least one surgery procedure in the last year for their treatment of persistent pain. Moreover, a majority of these individuals are not aware or have not attempted MBAA for their pain symptoms. Given these findings, as well as (1) the lack of access to qualified care for pain management within NF1, (2) lacking of empirically validated behavioral treatments for persistent pain

within NF1 and (3) an inability to empower individuals to take an active role in managing their condition, I believe by providing an empirically validated treatment in which individuals with NF1 can learn to self-manage their own pain symptoms, while learning new alternative treatments can provide tremendous potential and positive change for those living with persistent pain.

2. Anderson, L. and D. H. Gutmann (2015). Neurofibromatosis type 1. *Handbook of Clinical Neurology*, 132, 75-86.
3. Hirbe, C., & Gutmann, D. H. (2014). Neurofibromatosis type 1: a multidisciplinary approach to care. *The Lancet Neurology*, 13(8), 834-843.

3.1 Problem Statement

Adults with NF1 are currently using pharmacological interventions and 60% had at least one surgery procedure in the last year for their treatment of persistent pain. Moreover, a majority of these individuals are not aware or have not attempted MBAA for their pain symptoms. Given these findings, as well as (1) the lack of access to qualified care for pain management within NF1, (2) lacking of empirically validated behavioral treatments for persistent pain within NF1 and (3) an inability to empower individuals to take an active role in managing their condition, I believe by providing an empirically validated treatment in which individuals with NF1 can learn to self-manage their own pain symptoms, while learning new alternative treatments can provide tremendous potential and positive change for those living with persistent pain.

3.2 Purpose of Study/Potential Impact

We expect individuals with NF1 utilizing the iCanCope program to have decreased pain severity and interference if they regularly engage in the program. In addition, due to the added contingency management, we expect to see differences between the intervention groups (*iCanCope-NF* and *iCanCope-NF +CM*). By adding contingencies to increased engagement the CM grouping should have more improvements in pain intensity and pain interference in addition to current iCanCope processes. If we demonstrate initial feasibility and preliminary impact, in collaboration with Drs. [name] and [name], a definitive RCT will be conducted. In future studies, evaluating the sustainability of impact on the outcomes over the course of 12 months is critical to sustaining the impact of the application as well as generalization of treatment. Thus, following the patients in a 1, 3 and 6-month follow-up post-treatment is necessary.

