6.1 Intervention

6.1.1 Description of Intervention

Figure 1 presents a CONSORT study flow diagram. Potential participants will be required to access an online secure site to learn about the study and to be evaluated for eligibility, provide informed consent, and complete baseline assessments. Eligible participants will be randomly assigned to one of the 3 conditions: *iCanCope-NF*, *iCanCope-NF +CM*, or the Control Group (treatment as usual or TAU). Individuals in the *iCanCope* groups will receive 8 weeks of 24-hour access to the program.

The proposed architecture of the *iCanCope-NF* consists of four theory-based components, integrated across smartphone: self-monitoring (e.g. Real-time symptom tracking via patient self-report. Customizable graphs and reports; smart goal setting (e.g. Set

goals related to improving pain, sleep, mood, physical activity and social activity, Adherence to SMART' framework); personalized self-management instruction and rehearsal (e.g. (In-the-moment access to pain coping strategies, Personalized instruction based on goals); and detailed pain education (Provide information on types of pain, strategies for maintaining physical activity and strategies managing anxiety, stress and emotions).

iCanCope Orientation. At study intake, individuals within the *iCanCope-NF* and *iCanCope-NF* +Contingency Management (CM) groups will receive a 10-minute video orientation to the iCanCope program. The orientation will emphasize daily usage of the CBT treatment platform. Individuals will receive a login and password information, general information and instruction, and contact information for technical problems.

iCanCope-NF Group: In this group, individuals will receive the *iCanCope-NF program*. The intervention will be delivered on a restricted password-protected mobile application.

Participants will be encouraged to log onto the pain diary app (via automated alerts) once per day over the 8-week period to complete pain diary entries and develop and track their goals related to their pain, physical, social activities, sleep, as well as work through content based on their goals.

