6.3.6 End of Study and Follow Up

At the end of the study, all participants in each group (TAU, iCanCope, iCanCope+CM) will be required to complete the identical set of assessments at intake, minus demographic information. Individuals who prematurely left early or who withdrawn from the study will not be asked to complete the end of the study survey. Additionally, individuals with access to the iCanCope mobile application license will end and will not be able utilize the mobile application until the follow-up is complete. For individuals who did not have access to the iCanCope mobile application they will continue not having access to the mobile application.

All participants in each group will complete a 6-week post discharge follow-up. The follow-up will be identical to the discharge evaluation. Individuals will be emailed a secured email by the research assistant to complete the survey one day before the 6-week survey. All participants will have a one-week (7days) to complete the assessment, and a reminder email will be sent on the last day of the survey to the participants. Individuals will not be required to complete but will be encouraged to do so.

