6.4.3.2 Secondary Objectives Analyses, if applicable

Secondary analyses will explore three research questions: (1) Does smartphone program (*iCanCope-NF*) compared with control condition lead to differences in pain and pain-related activity limitations, sleep functioning, emotional functioning (depression, anxiety), pain catastrophizing, self-efficacy, knowledge, psychological flexibility immediately post-treatment (T2)? This will be evaluated by incorporating an estimating equation approach to understand the differences in scores and using a sequential multilevel logistic regression models to estimate the independent and combined effects of proposed time-varying (contextual) variables on the probability of pain levels. We will also test interaction effects between stable/trait-level participant characteristics and contextual variables. (2) Does the *iCanCope-NF + CM* increase the usage of the *iCanCope-NF* program as compared to *iCanCope-NF* without CM, and do their corresponding levels of pain and pain-related activity decrease? This will be evaluated between the two intervention groups and using the difference in nominal data sets, and simple qualitative analyses. (3) Do individuals with NF1 utilize the MBAA more readily because they are on the mobile application? To assess the moderation effect, we will include an interaction term for each separate moderator variable and key predictor of interest (two-way interaction between moderator and group for cross-sectional analysis and three-way interaction between moderator, group and time for longitudinal analysis) in the regression models and test its significance using Wald t-test.

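### Pain at the 6-week follow-up is planned only as within-group change, so the trial gives no randomised estimate of whether a T2 difference persists

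*Combined protocol and SAP*

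**What the plan says.** - **Treatment and visits.** Section 6.1.1 says the app "groups will receive 8 weeks of 24-hour access to the program". Section 6.3.6 then says "All participants in each group will complete a 6-week post discharge follow-up", and "The follow-up will be identical to the discharge evaluation". App licences in the two app arms stay closed until that visit is done, and controls continue without access. Completion is optional: "Individuals will not be required to complete but will be encouraged to do so".
- **Primary pain outcomes (5.2.1).** BPI-SF severity and the Pain Interference Index are each described as a within-group change, with a time frame through study completion, on average 4 months.
- **App versus control (6.2.1, 6.4.3, 6.4.3.2).** The list of outcomes in this question ends with "knowledge, psychological flexibility immediately post-treatment (T2"). The method is an estimating-equation approach plus multilevel logistic models.
- **Entry (5.3.2).** Participants need a BPI-SF interference score of three or more.
- **Durability.** The background (2.1) states that "the skills learned through CBT continue, sometimes even increase, after treatment has been completed". Section 3.2 says "In future studies, evaluating the sustainability of impact on the outcomes over the course of 12 months is critical" and adds that "following the patients in a 1, 3 and 6-month follow-up post-treatment is necessary". It also says that a definitive RCT will follow if feasibility and preliminary impact are shown.

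**The concern.** The treatment rationale is that participants acquire skills they keep. The 6-week visit, with the app closed to the app arms, is the one point in this trial where randomised groups could be compared on that. The plan collects the data but names no arm difference there. The between-arm result on pain would therefore be the same whether a T2 difference faded after access ended or lasted.

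Within-group change does not fill the gap. Participants enter because their interference score is at or above a threshold, so scores on that measure, and on pain measures correlated with it, are expected to drift down in every arm without any treatment effect. A sustained fall in an app arm could be lasting benefit, regression to the mean, or both. The decision on a definitive RCT would then be taken without a randomised estimate of persistence that this trial could supply from data it already collects.

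**Working it through.** **1. Does the primary time frame reach the follow-up visit?** Access lasts 8 weeks (6.1.1) and follow-up comes 6 weeks after discharge (6.3.6): 8 + 6 = 14 weeks, and 14 / 4.345 = 3.2 months. With the 7-day completion window it is 15 / 4.345 = 3.5 months. T2 falls at 8 / 4.345 = 1.8 months. A time frame averaging 4 months therefore takes in follow-up.

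**2. Which planned analysis gives an arm difference in pain at that visit?**

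| Analysis | Section | Arm difference in pain at 6 weeks? |
|---|---|---|
| Primary pain outcomes | 5.2.1 | No: within-group change |
| Mixed model, AR(1) | 6.4.3.1 | No: engagement and activities tried |
| App versus control | 6.2.1, 6.4.3, 6.4.3.2 | No: T2 only |
| CM versus no CM | 6.4.3.2 | Not specified: no visit named |
| Moderator by group by time | 6.4.3.2, question 3 | Not specified: no visits named, and the term tests moderation |

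**3. How precise would a follow-up contrast be?** The plan gives no effect size, SD or power to reproduce, so this is illustrative. The inputs are 36 per arm (6.4.2, already net of the plan's 20% attrition), two-sided 0.05, 80% power and SD = 1. For one pairwise contrast without baseline adjustment, d = (1.960 + 0.842) × sqrt(2/n).

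- n = 36: 2.802 × sqrt(2/36) = 0.66.
- n = 28 (assumed further 20% loss; 36 × 0.8 = 28.8, rounded down): 2.802 × sqrt(2/28) = 0.75.
- For losses of 10% and 30% (n = 32 and 25): 0.70 and 0.79.
- Power for an assumed d = 0.5 is 56% at n = 36 and 46% at n = 28.

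Baseline adjustment multiplies d by sqrt(1 − r²), where r is the correlation between visits. That factor is 0.87 at r = 0.5 and 0.71 at r = 0.7.

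**4. How precise is the change from T2?** Assume equal variances and one common correlation r among the three visits, with complete data. The baseline-adjusted T2 score has variance 1 − r². The change from T2 to follow-up has variance 2(1 − r); baseline adjustment does not reduce it, because its covariance with baseline is r − r = 0.

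| r | T2, 1 − r² | Change, 2(1 − r) | Ratio |
|---|---|---|---|
| 0.5 | 0.75 | 1.00 | 1.33 |
| 0.6 | 0.64 | 0.80 | 1.25 |
| 0.7 | 0.51 | 0.60 | 1.18 |

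The change from T2 thus has 18% to 33% more variance than the T2 contrast, before any extra loss at an optional visit.

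**5. What would the missing-data rule do?** Section 6.4.5 codes missing data as zero. Both pain scales start at 0 and higher is worse (5.2.1), so zero is the best score. If two arms share a true mean m but lose fractions p1 and p2 at random, their coded means differ by (p1 − p2) × m. Assumed losses of 30% and 10% give a spurious difference of 0.2m.

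**6. Is control access settled before the visit?** Section 6.3.6 has controls continuing without the app. The control-group text in 6.1.1 offers it after the trial, labelled T2, and also after the study is over. Section 6.3.6 itself places the discharge assessment at the end of the study, so the wording leaves the start of control access unclear.

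**The case against.** The strongest defence is that this is a pilot whose stated primary question is feasibility (6.2.1) and that section 3.2 assigns sustainability to future studies over 12 months. Keeping the arm comparison at T2 is consistent with that. This stands, and it limits the point to an improvement. A reader might infer that the plan calls durability critical for this trial and then ignores it; the words "In future studies, evaluating the sustainability of impact on the outcomes over the course of 12 months is critical" do not support that.

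A reader might also infer that the follow-up data enter no treatment comparison at all. That goes too far. The CM question has no time limit, and the moderator by group by time term is labelled longitudinal. Follow-up data could enter either, though neither is specified to use them. Nor are the data unplanned: the primary time frame covers them, and a return to baseline within an app arm would be visible. What that leaves missing is the comparison with control.

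Finally, a reader might expect the extra visit to buy precision. Under the model above, the mean of T2 and follow-up would have less variance than T2 alone. But an average over the two visits does not measure persistence, and the change from T2, which does, is the less precise quantity.

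**Conclusion.** The point holds as a gap in specification. All arms have an identical 6-week assessment, pain at that visit is addressed explicitly only as within-group change, and no between-arm contrast there is named. Given the entry threshold, the plan as written gives no randomised estimate of whether a T2 difference persists. It is not an internal contradiction, and it does not affect the T2 comparison.

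The contrast would be an estimate with an interval, not a powered test: about 0.66 SD detectable at 36 per arm and 0.75 SD at 28, assuming two-sided 0.05, 80% power and no baseline adjustment. The further 20% loss behind the second figure is an assumption, as are the correlations of 0.5 to 0.7 behind the 18% to 33% extra variance of the change from T2. The value of the contrast also depends on two matters in the documents: the zero-coding rule and the timing of control access.

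**What to change.** In 6.4.3.2, fit the planned estimating-equation model to both post-baseline visits, with baseline adjustment and an arm-by-visit term. Keep T2 as the main contrast. For BPI-SF severity and the Pain Interference Index, prespecify the 6-week arm difference and its change from T2, with confidence intervals and labelled exploratory. Define the visit labels (T1, T2, T3) once.

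Two further edits are needed for the contrast to be interpretable:

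- **Missing data (6.4.5).** Do not code missing follow-up scores as zero. Use the observed data in a model that handles missingness, state its assumption, and add a sensitivity analysis.
- **Control access (6.1.1 and 6.3.6).** Reconcile the two statements on when controls may receive the app, since access before the 6-week visit would confound the contrast.

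The cost is a short addition to the analysis text and these two edits; no new data are needed. The downsides are an additional follow-up contrast to account for under the multiplicity statement in 6.4.1, probably more missing data than at T2 because the visit is optional, and limited precision.
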